9 STATISTICS

9.1 Sample Size Determination

As the primary aim of this study is to demonstrate safety, there was no power analysis conducted. Attrition factors include death from stroke but not treatment (10%), fluid overload (20%) and early discharge (5%).

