9.3.3 Analyses of Safety and Efficacy

All efficacy results will be examined using both ITT and per protocol populations. Although the trial's main purpose is to demonstrate safety, several measures of efficacy will be examined in order to provide effect size estimates for a appropriately powered future trial demonstrating efficacy. As such, both pairwise comparisons at various timepoints and longitudinal data will be examined.

- 1) Primary efficacy outcome
- 2) Secondary efficacy outcomes, as specified in the order presented below

Outcome	Statistical Analysis Methods
Primary	All analyses will be accomplished using SAS Software 9.4 (SAS Inc. Cary, NC). Primary: The frequency of SAEs, SAEs resulting in death, AEs, and discontinuations due to AEs will be summarized as counts and percentages between conditions. Comparisons will be conducted using Fisher's Exact tests.
Secondary	
Secondary: Comparisons between conditions for mRS will be evaluated using generalized mixed modeling assuming a binomial distribution (0-6) with sandwich estimation nested by site and participant, when applicable. Pairwise comparisons of mRS will be conducted at day 90 using a Dunnett correction. In addition, simple and interaction effects between pre-stroke, discharge, 30 and 90-day mRS by condition will be examined. Because superiority over placebo and lower dose is hypothesized, testing will reflect this superiority framework with one-tailed tests.
 
Both NIHSS score and BI at Day 90 will be examined in a similar fashion assuming a binomial distribution (0-42 & 0-100) with sandwich estimation nested by site and participant (when applicable). Pairwise comparisons between conditions will be conducted at day 90 using a Dunnett correction. In addition, simple and interaction effects between pre-treatment, discharge, 30 and 90-day NIHSS scores and BI by condition will be examined. Because superiority over placebo and lower dose is hypothesized, testing will reflect this superiority framework with one-tailed tests.
 
Mortality will be examined using Kaplan-Meier estimation with pairwise comparisons with a Dunnett correction with censoring on last known follow up. Because superiority over placebo and lower dose is hypothesized, testing will reflect this superiority framework with one-tailed tests. Marginal Cox Hazard regression will also be used to evaluate mortality with sandwich estimation and nesting within site.

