1 INTRODUCTION

The purpose of this statistical analysis plan (SAP) is to provide a description of the statistical methods to be implemented for the analysis of data from the study with protocol number 06.5.1.H1 dated 09 May 2022 (version 2.4). The SAP will be finalized prior to database lock. Any future addendum to the SAP (if applicable) will be referenced in the Clinical Study Report (CSR).

The SAP will be considered as the governing document and in case of any differences between this SAP and the study protocol, the SAP will supersede the protocol.

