3.4 Safety and Efficacy Assessments

The primary safety analysis will be conducted in the Safety Population. The secondary efficacy analysis will be conducted in the ITT and PP Populations.

3.4.1 *Primary Safety Endpoints*

Frequencies and severities of SAEs

The proportion of participants with SAEs through Day 90 between the three treatment groups (RNS60 0.5 mL/kg/h, RNS60 1.0 mL/kg/h, and placebo 1.0 mL/kg/h)

In addition, the frequency and severity categories will be summarized with counts and percentages of SAEs by treatment and site and in total. See Appendix C for definition of SAE.

90-day Mortality

The proportion of participants alive at Day 90 between the three treatment groups (RNS60 0.5 mL/kg/h, RNS60 1.0 mL/kg/h, and placebo 1.0 mL/kg/h).

3.4.2 *Secondary Efficacy Endpoints*

All outcomes will be assessed in the following hierarchical order (to control of the overall Type I error rate). As it is hypothesized that higher dosage will result in less disability, subjects receiving placebo 1.0 mL/kg/h will first be compared to RNS60 1.0 mL/kg/h and then, as a lower ranking secondary endpoint, combined RNS60 doses (1.0 mL/kg/h and 0.5 mL/kg/h) compared to placebo, and finally RNS60 0.5 mL/kg/h compared to placebo. Specifically, efficacy of each of the 5 key endpoints will be assessed between high-dose RNS60 compared to placebo, followed by the same endpoints between combined RNS60 doses (1.0 mL/kg/h and 0.5 mL/kg/h) compared to placebo, finally followed by the same 5 endpoints between RNS60 low dose (0.5 mL/kg/h) compared to placebo:

1. Disability based on mRS score, high-dose vs placebo
2. Infarct progression/regression, high-dose vs placebo
3. NIHSS score, high-dose vs placebo
4. Worsening of stroke high-dose vs placebo
5. BI, high-dose vs placebo
6. Disability based on mRS score, combined-dose vs placebo
7. Infarct progression/regression, combined-dose vs placebo
8. NIHSS score, combined-dose vs placebo
9. Worsening of stroke, combined-dose vs placebo

10. BI, combined-dose vs placebo
11. Disability based on mRS score, low-dose vs placebo
12. Infarct progression/regression, low-dose vs placebo.
13. NIHSS score, low-dose vs placebo
14. Worsening of stroke, low-dose vs placebo
15. BI, low-dose vs placebo

If a comparison listed above is determined to be not statistically significant, then the remaining comparisons in the hierarchy will be tested in any case and interpreted in an exploratory manner.

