3.5.1 Adverse Events (AEs)

An AE is defined as any untoward medical occurrence in a subject or clinical investigation participant administered a pharmaceutical product and which does not necessarily have to have a causal relationship with this treatment.

An AE can therefore be any unfavorable and unintended sign (including an abnormal laboratory finding, for example), symptom or disease temporally associated with the use of a medicinal product, whether or not considered related to the medicinal product. AEs will be captured from the start of study drug infusion through study completion (Day 90). All AEs will be coded to system organ class and preferred term using MedDRA version 24.0. A medical review of the coding reports will be performed prior to database lock. Treatment-emergent adverse events (TEAEs) are defined as AEs that start after the study drug infusion.

The investigator will grade the intensity of the AE as mild, moderate, or severe.

The relationship of an AE to study drug will be assessed as related, possibly related, or unrelated.

An overview of AEs will be provided including counts and percentages of subjects (and event counts) with the following:

- Any TEAEs (overall and by maximum severity)
- Any study drug related TEAEs (overall and by maximum severity)
- Any SAEs
- Any treatment-emergent serious AEs (TESAEs)
- Any study drug related TESAEs
- Any TEAEs leading to discontinuation of study drug infusion
- Any AEs leading to death
- TEAE occurrence by Month (Day 0-Day 7, Day 8 – Day 14, Day 15 – Day 21, Day 22 – Day 30, Day 31-Day 60, and Day 61-Day 90)

Counts and percentages of subjects (and event counts) will also be presented by system organ class and preferred term for each of the categories in the overview. If more than one event occurs with the same preferred term for the same subject, the subject will be counted only once for that preferred term using the most severe occurrence for the summary by severity. The number of events will be presented for overall category of TEAE and for each system organ class and preferred term. The number of events will not be presented for each category of maximum severity. AE listings will include the following information:

- Subject ID
- Adverse event term
- Adverse event preferred term
- System Organ Class
- Start date
- Outcome
- End date
- Relationship to study drug
- Action taken with study drug

- Severity
- SAE Criteria

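### Neither primary safety endpoint has a planned between-arm estimate or interval, so the plan does not quantify what excess in SAEs or deaths has been ruled out

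*SAP*

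**What the plan says.** Both documents make safety the primary aim, judged on SAEs and 90-day mortality. Protocol 9.1 gives this as the reason for not sizing the trial: "As the primary aim of this study is to demonstrate safety, there was no power analysis conducted". The target is 100 participants allocated 1:1:1.

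SAP 3.4.1 covers the two primary endpoints with two incomplete sentences: "The proportion of participants with SAEs through Day 90 between the three treatment groups" and "The proportion of participants alive at Day 90 between the three treatment groups". It then adds that "the frequency and severity categories will be summarized with counts and percentages of SAEs by treatment and site and in total". SAP 3.5.1 adds further tabulation: "An overview of AEs will be provided including counts and percentages of subjects (and event counts) with the following". Nothing in either section names a contrast, a test, a risk difference or ratio, or an interval.

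In Protocol 9.3.3, the primary row has SAEs, fatal SAEs, AEs and discontinuations due to AEs summarised as counts and percentages, and then says "Comparisons will be conducted using Fisher's Exact tests". The secondary (efficacy) row of the same table adds Kaplan-Meier comparisons of mortality with a Dunnett correction, one-tailed. It also says "Marginal Cox Hazard regression will also be used to evaluate mortality with sandwich estimation and nesting within site".

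On precedence, SAP section 1 states that "in case of any differences between this SAP and the study protocol, the SAP will supersede the protocol". SAP 6.4 reports no significant change from the protocol's analyses beyond the ITT definition, the specification of analysis types and further definition of endpoints.

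**The concern.** A trial meant to show safety has to say how large a harm its data are compatible with. Percentages by arm leave that to the reader. A Fisher test of no difference does not answer it either, because failing to reject equality in a small sample excludes very little.

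The SAP is more specific elsewhere. In 3.4.2, mRS, infarct volume and worsening of stroke get between-arm estimates with 95% intervals, and NIHSS and the Barthel Index get between-arm differences or odds ratios. In 3.5.3, even the maximum blood-pressure deviation gets a 95% interval for each comparison. The two endpoints that carry the primary objective get neither.

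At stake is the main conclusion of the trial. Without an estimate and interval, a report that follows the plan cannot state the excess in SAEs or deaths that has been excluded. The designers of a later efficacy trial would need that figure.

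**Working it through.** **Is there a stated figure to reproduce?** No. Neither document gives a power, a detectable difference, a margin or a precision for these endpoints. The only input is the target: 100 / 3 = 33.3, so about 33 per arm and 67 for the two doses combined. The Safety Population can only be this size or smaller.

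**Assumptions.** The documents give no SAE rate. The 10% for stroke death (Protocol 9.1, SAP 2.2.4) is an attrition figure, not a control-arm mortality rate. Control rates of 10% to 30% are therefore assumed. Fisher's test is taken as pairwise and two-sided at 0.05, because the protocol does not state its form.

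**Power.** Power is the sum of Bin(x; 33, p1) × Bin(y; 33, p2) over all pairs (x, y) with Fisher p ≤ 0.05.

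| Placebo | RNS60 arm | Excess (points) | Power, 33 v 33 |
|---|---|---|---|
| 10% | 20% | 10 | 11.5% |
| 15% | 30% | 15 | 21% |
| 20% | 40% | 20 | 32% |
| 30% | 50% | 20 | 32% |

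If the test is instead the three-group exact test, with the third arm at either the placebo rate or the raised rate, power is 17-18%, 28-30%, 40-43% and 36-37% for the same four rows. It is higher, but still low.

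**What an interval would show.** The Newcombe interval is built from Wilson limits (l, u) for each arm. With d = p2 - p1:

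- lower = d - √[(p2 - l2)² + (u1 - p1)²]
- upper = d + √[(u2 - p2)² + (p1 - l1)²]

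The Wilson limits are 0.0665 to 0.3092 for 5/33 (p = 0.1515) and 0.1738 to 0.4734 for 10/33 (p = 0.3030).

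*10/33 on RNS60 against 5/33 on placebo:*

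- d = 0.1515
- lower = 0.1515 - √(0.1292² + 0.1577²) = 0.1515 - 0.2039 = -0.052
- upper = 0.1515 + √(0.1704² + 0.0850²) = 0.1515 + 0.1904 = +0.342
- Fisher p = 0.24

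*5/33 in both arms:* d = 0, and the half-width is √(0.1577² + 0.0850²) = 0.179, so ±18 points.

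Other cases by the same formulas:

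| RNS60 v placebo | Fisher p | Risk difference (points) | 95% CI (points) |
|---|---|---|---|
| 3/33 v 3/33 | 1.00 | 0 | -15.7 to +15.7 |
| 7/33 v 3/33 | 0.30 | +12.1 | -5.8 to +29.7 |
| 10/33 v 3/33 | 0.061 | +21.2 | +1.8 to +39.3 |
| 10/33 v 10/33 | 1.00 | 0 | -21.4 to +21.4 |
| 7/67 v 3/33 (combined) | 1.00 | +1.4 | -14.1 to +12.6 |
| 20/67 v 10/33 (combined) | 1.00 | -0.5 | -20.0 to +17.1 |

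In the third row, deaths more than triple while the Fisher p-value stays above 0.05. The interval lies wholly above zero.

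**The case against.** The strongest reply has four parts.

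1. **Fisher is not the protocol's only mortality method.** This is correct: Kaplan-Meier and a marginal Cox model are also planned, and a Cox model yields an effect estimate. The protocol also sets a general 95% level for interval estimates. These do not close the gap. Both analyses are listed as efficacy, and the Kaplan-Meier test is one-tailed toward benefit. No hazard ratio or interval is named as an output, neither analysis reaches the SAP, and neither concerns SAEs.

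2. **The SAP names no test, so under the SAP alone there is no significance result to misread.** This also stands. If the SAP's silence replaces the protocol, no comparison remains. If it leaves the protocol in force, Fisher and Cox both return. Neither reading quantifies an SAE excess, and the documents do not settle which applies.

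3. **A reader might infer that non-significance will be declared as safety.** The documents do not say so. They contain no decision rule at all. Safety will also be judged from unblinded DSMB review, AE tables by severity and relatedness, laboratory data, QTcF categories and a blood-pressure model with intervals. The defect is the missing criterion, not a wrong one.

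4. **The trial is an openly unpowered proof of concept, and anyone can compute the interval from the published counts.** This is true, and it limits how serious the point is. It does not explain why the primary comparison should be left to the reader.

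**Conclusion.** The concern holds in this form: SAP 3.4.1 specifies no between-arm comparison, effect estimate or interval for participants with SAEs or for death by Day 90. The protocol's primary row supplies only a Fisher test of unstated form. As written, the plan does not say what excess has been ruled out.

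The size depends on assumed rates. Over control rates of 10% to 30% with 33 per arm, pairwise power for 10- to 20-point excesses is 11.5% to 32%. Equal event counts of 3, 5 or 10 per arm leave intervals of about ±16 to ±21 points. The alternative three-group form of Fisher's test does not change the conclusion.

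Two broader readings are not supported. It is not true that every efficacy endpoint gets an interval: EQ-5D-5L is listed as a secondary endpoint but has no planned estimate in SAP 3.4.2. Nor is the sample size itself the fault, since both documents disclose that it was not based on power. The point concerns how the primary result is reported, and it is a worthwhile, inexpensive correction.

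**What to change.** In SAP 3.4.1, for participants with at least one SAE and for death by Day 90 in the Safety Population:

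- Report the risk difference against placebo for each RNS60 dose and for the combined doses, with a 95% interval by a named method (Newcombe or Miettinen-Nurminen).
- Word the safety conclusion as the excess that the upper limit excludes, and state that a non-significant test is not evidence of safety.
- Keep Fisher's test as descriptive only, and state whether it is three-group or pairwise and whether it is one- or two-sided.
- Say whether the protocol's Cox mortality analysis is retained.

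The cost is a few SAP lines and one table, from data already collected. The downside is a less favourable safety statement: even with equal event rates, the upper limits will probably be well above 10 points.

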3 TRIAL OBJECTIVES

3.1 Objectives

Table 3-1: Objectives and Outcomes

Objectives	Outcomes
Primary – Safety	
To determine the safety based on SAEs	Proportion of participants with SAEs to Day 90
90-day mortality	Proportion of participants alive at Day 90
Secondary – Efficacy	
Reducing global disability in participants with AIS	Mean mRS score
Reducing mortality rate	Median or proportion of death on survival curve
Improving neurological outcome	Mean NIHSS score at discharge
Reducing worsening of stroke	See 3.1.2
Reducing functional dependence	Mean BI at Day 90
Tertiary/Exploratory	
Decreasing infarct volume	Volume of stroke as measured by MRI brain imaging
Improving health related quality of life	EQ-5D-5L at Day 90

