2.3 Study Endpoints

2.3.1 Primary Safety Endpoints

The primary safety endpoints include:

- 1) Frequencies and severities of SAEs (see Appendix C for definition of SAE).
- 2) 90-day mortality (as a proportion).

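### The severity part of the primary SAE endpoint is summarised per event, and no planned summary counts patients by their worst SAE

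*SAP*

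**What the plan says.** SAP 2.3.1 lists as the first primary safety endpoint "Frequencies and severities of SAEs (see Appendix C for definition of SAE"; protocol 3.2.1 likewise names both frequency and severity. SAP 3.4.1 then plans two SAE outputs.

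- **Occurrence**, per participant: "The proportion of participants with SAEs through Day 90 between the three treatment groups". This matches the outcome in protocol Table 3-1, "Proportion of participants with SAEs to Day 90", which does not mention severity.
- **Severity**, introduced as an addition: "the frequency and severity categories will be summarized with counts and percentages of SAEs by treatment and site and in total". The unit changes from participants to SAEs, and no denominator is given.

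SAP 3.5.1 works per subject: "An overview of AEs will be provided including counts and percentages of subjects (and event counts) with the following". The first row reads "Any TEAEs (overall and by maximum severity", and the drug-related TEAE row has the same qualifier. The serious-event rows, such as "Any treatment-emergent serious AEs (TESAEs", do not. The dedicated SAE listing shows severity, but a listing is not a summary.

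**The concern.** Patients are randomised and treated; SAEs are not. SAEs may cluster within patients, and the number of SAEs in an arm may depend on treatment. A percentage of SAEs therefore has a denominator determined after randomisation. An arm that adds mild or moderate SAEs will show a smaller severe share even if more of its patients have a severe SAE. In an arm of about 33, one patient with a run of complications can also carry much of the table.

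At stake is how one component of a primary endpoint is described, in a trial whose stated purpose is safety. The usual question for that component is how many patients in each arm had a severe SAE, and no planned summary answers it.

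**Working it through.** **Inputs from the documents.** Target 100 participants (SAP 2.2.4) allocated 1:1:1 (SAP 2.2.1), so 100/3 = 33.3, or about 33 per arm if nearly all are treated. Severity grades are mild, moderate and severe (SAP 3.5.1). The safety denominator is randomised subjects who received any study drug, by treatment received (SAP 3.2.5). The documents give no SAE rate, severity mix or events per patient, so there is no planned figure to reproduce. All counts below are assumed.

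**Formulas.**
- Event share = severe SAEs / all SAEs in the arm.
- Patient proportion = patients with at least one severe SAE / Safety Population patients in the arm.

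**Illustration 1.** Placebo: 10 SAEs in 10 patients, 5 of them severe. RNS60: 20 SAEs in 15 patients, 7 severe, in 7 different patients.

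| | Placebo | RNS60 | RNS60 appears |
|---|---|---|---|
| Severe share of SAEs | 5/10 = 50% | 7/20 = 35% | milder |
| Patients with a severe SAE | 5/33 = 15% | 7/33 = 21% | worse |
| Patients with any SAE | 10/33 = 30% | 15/33 = 45% | worse |
| Severe SAEs, raw count | 5 | 7 | worse |

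The percentage points the wrong way; the other planned quantities do not.

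**Illustration 2, built so that the other summaries give no warning.** Placebo: 4 patients with two severe SAEs each, 6 patients with one non-severe SAE each, and 3 further patients with a severe non-serious TEAE. RNS60: 7 patients with one severe SAE each, 2 patients with two non-severe SAEs each and 1 with three.

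| | Placebo | RNS60 |
|---|---|---|
| Severe share of SAEs | 8/14 = 57.1% | 7/14 = 50.0% |
| Patients with any SAE | 10/33 | 10/33 |
| Patients with any severe TEAE | 7/33 | 7/33 |
| Patients with a severe SAE | 4/33 = 12.1% | 7/33 = 21.2% |

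Here both the count and the share of severe SAEs fall, any-SAE occurrence ties and TEAE maximum severity ties. Only the unplanned patient-level row shows the increase. Fisher's exact test on that row gives two-sided p = 0.51, so what is lost is the direction of a description and not a significant result.

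**How often the share misleads.** Simulation, 20,000 runs per setting, 33 per arm. Severe-SAE patient rates of 10% vs 20%; each such patient has one severe SAE plus a Poisson number with mean 0.3; placebo has a mean of 0.3 non-severe SAEs per patient. Among runs in which more RNS60 patients than placebo patients had a severe SAE, the event share was lower on RNS60 in 10%, 38% and 65% of runs when the RNS60 mean of non-severe SAEs was 0.3, 0.6 and 1.0. Across all rate pairs tried, the range was 10% to 78%. The spread shows that the result depends on the assumptions.

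**The case against.** **The sponsor may mean subjects.** SAP 3.1.4 says that categorical data are generally summarised by subject with a clearly defined denominator. SAP 3.5.1 counts a subject once per preferred term at the worst severity and does not show event numbers by maximum-severity category. This has weight: the event denominator is a literal reading and is not stated. But the rule in 3.1.4 is a general one that admits exceptions, and 3.4.1 changes from participants to SAEs between adjacent outputs. If subjects are meant, 3.4.1 still has to say so and say how a patient with several SAEs is classified.

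**Harm would usually be seen anyway.** This largely stands. In Illustration 1, participants with any SAE (10 vs 15), total SAEs (10 vs 20) and severe SAEs (5 vs 7) all show RNS60 worse. Any-SAE occurrence, 90-day mortality and TEAE maximum severity are per participant, and in arms of about 33 the SAE listing can be read patient by patient. It took a constructed case to make count and share mislead together.

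**A stronger reading to avoid.** Protocol 9.3.3 says "discontinuations due to AEs will be summarized as counts and percentages between conditions. Comparisons will be conducted using Fisher's Exact tests". A reader might infer that Fisher's test will be run on the event-level severity table, where clustering would violate independence and inflate the false-positive rate. The documents do not support this. The protocol attaches the test to the frequency of SAEs, fatal SAEs, AEs and discontinuations, not to severity. SAP 3.4.1 names no test for the severity table, and the SAP supersedes the protocol where they differ.

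**Conclusion.** The point holds as a minor one and a cheap improvement. Read literally, the severity component of a primary safety endpoint is summarised per event without a stated denominator, and no planned summary gives patients by worst SAE severity. The severe share of SAEs can then move opposite to the number of patients with a severe SAE (50% to 35% against 15% to 21% in Illustration 1).

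The size is limited to the direction of one descriptive table. No error rate, sample size or planned test changes, and the occurrence and mortality components are unaffected. The numerical examples rest on assumed SAE counts and on 33 treated patients per arm. The structural gap rests only on the wording of SAP 3.4.1 and 3.5.1.

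**What to change.** In SAP 3.4.1, replace the event-based severity summary with this: each Safety Population participant is classified once by the maximum severity of any SAE through Day 90 (none, mild, moderate, severe); counts and percentages use the Safety Population participants in that arm, by treatment received, as denominator; numbers of SAEs are shown alongside without percentages. In SAP 3.5.1, extend the overall-and-maximum-severity split to the SAE and TESAE rows.

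The cost is SAP wording and one reprogrammed table. Protocol 10.3.2 already requires an intensity grade for every SAE, and the maximum-severity derivation already exists for TEAEs. The small downside is that repeat events in one patient appear only in the event counts.
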